9.2. Definition of study populations

9.2.1. Phase I (Dose escalation part)

The following patients will not be included in the population assessable for safety (primary analysis) and thus will be replaced:

- Patients who received \leq 75% RDI (Relative Dose Intensity) for trabectedin OR \leq 75% RDI for durvalumab over cycle 1, due to drug-related AE not considered as DLT.
- Patients who goes off treatment over cycle 1 for reasons unrelated to toxicity (DLT or any other AE), e.g. progression, lost to follow-up, will be replaced

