3.2. DEFINITIONS

Dose-limiting toxicity (DLT):

A DLT is defined as an AE or laboratory abnormality that fulfills all the criteria below:

- Begins on the first 21 days of treatment.
- Is considered to be at least possibly related to the study treatment.
- Meets one of the criteria below, graded as outlined or according to NCI-CTCAEv4.03 :
 - Any grade-4 toxicity (except for vomiting without maximal symptomatic/prophylactic treatment and if toxicity is transaminitis, but which have to be resolved at Day 21, i.e. return to Baseline or grade 1).
 - Grade-3 non-haematological toxicity lasting > 7days (except for 1rst episode of nausea and if toxicity is transaminitis, which have to be resolved at Day 21, i.e. return to Baseline or grade 1).
 - Grade-3 hematologic toxicity lasting for > 7days.
 - Grade 4 neutropenia with fever.
 - Grade > 2 thrombocytopenia with bleeding.

DLT status:

In addition, the steering committee will resolve any specific issue regarding the DLT status (see section 12.1.1).

Maximum tolerated dose (MTD):

The MTD is defined as the highest dose at which no more than 1 in 6 patients in the cohort experience a DLT in the first 21 days. The conclusions of the steering committee for the definition of

of the MTD will be submitted for approval to an independent data monitoring committee (IDMC) before opening the expansion cohorts.

Recommended phase II dose (RP2D):

The RP2D dose corresponds to the dose level to be recommended for further investigations in phase II trials. The RP2D dose for trabectedin when given in combination with Durvalumab, will be identified by the steering committee based on safety data from patients included in the dose escalation part and the expansion cohorts, as well as PD data. Data from all patients (dose escalation trial and expansion cohorts) will be used to define the RP2D.

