3.3.2. Dose levels

Dose escalation study assessing 3 doses level of Trabectedin given in combination with durvalumab (fixed dose).

Level	-1	1	2	3
Trabectedin (3h)	0.8 mg/m ²	1 mg/m ²	1.2 mg/m ²	1.5 mg/m ²

- The starting dose of Trabectedin is 1 mg/m².
- The maximum dose of Trabectedin administered (1.5 mg/m²) will not be exceeded.
- Patients will be allocated to 3 doses levels following a 3 + 3 design.
- A minimum of 3 patients and a maximum of 6 patients will be entered on each dose level.
- All 3 patients within a dose level will be observed during 21 days (the period of observation of DLTs) before accrual to the next higher dose level may begin.
- Dose escalation will proceed according to the following scheme:

Number of patients with DLT at one dose level	Escalation Decision Rule
0 out of 3	Enter 3 patients at the next dose level.
≥2	Dose escalation will be stopped. This dose level will be declared as the maximum administered dose (MAD). Three additional patients will be entered at the next lowest dose level if only 3 patients were treated previously at that dose.
1 out of 3	Enter at least 3 more patients at this dose level. 
• If 0 of these 3 patients experience DLT, proceed to the next dose level.• If 1 or more of this group suffer DLT, dose escalation will be stopped, and this dose is declared as the MAD. Three additional patients will be entered at the next lowest dose if only 3 patients were treated previously at that dose.
≤1 out of 6	This will be the maximum tolerated dose (MTD).

- As described above, the maximum administered dose (MAD) for Trabectedin is the dose in which ≥2/3 or ≥2/6 patients experience DLT.

- If the MAD for Trabectedin is seen at the starting dose level, then dose level “-1” will be the recommended dose.
- The MTD for Trabectedin is defined as the highest dose at which no more than 1 in 6 of the patients in the cohort experienced a DLT during the period of observation of DLTs.
- The steering committee will meet before proceeding or not to each dose escalation. In addition, the steering committee will be consulted to resolve any specific question regarding the DLT status (see section 12.1.1).
- Conclusions of the steering committee for the definition of MTD will be submitted for approval to an independent data monitoring committee (IDMC) before opening the expansion cohorts.

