4.4. Definitions of duration of Study and Treatment (Per Patient)

Patients will receive study treatment as long as it is considered to be in their best interest. Patients will be evaluated at scheduled visits in up to three study periods:

- **Pre-treatment (PRE TT):** from signature of informed consent to the first administration of study drugs.
- **Treatment (TT):** from the first administration of study drugs to treatment discontinuation.
- **Follow-up (FUP):** after treatment discontinuation, patients will be followed up four weeks later for toxicities, and beyond if grade 3 or 4 toxicity, until resolution.

Patients who discontinue treatment *without progression* will be **followed every 12 weeks** until:

1. Disease progression,
2. Initiation of other antitumor therapy,
3. Death, or
4. The date of study termination, whichever occurs first.

After documented progression or start of a new antitumor therapy, patients will be **followed every 6 months until:**

1. Death, or
2. The date of study termination, whichever occurs first.

Patients will be considered to be **on-study** from the signature of the informed consent to the end of follow-up period.

Patients will be considered to be **on-treatment** for the duration of their treatment until 30 days (4 weeks) after the last treatment administration, except if the patient starts a new antitumor therapy before this period.

Patients may withdraw their consent at any time; no further study activities will be conducted on them.

Treatment discontinuation occurs when an enrolled patient ceases to receive the study medication or starts a new antitumor therapy, regardless of the circumstances, and is defined as 30 days after the day of the last treatment administration, unless the patient starts a new antitumor therapy, in which case the date of administration of this new antitumor therapy will be considered the date of treatment discontinuation. The primary reason for any discontinuation will be recorded on the patient's case report form (CRF). If a patient discontinues treatment, every effort should be made to complete the scheduled assessments. Administration of the study treatments should be permanently discontinued if this is considered to be in the best interest of the patient. More specifically, treatment will be discontinued due to any of the following reasons:

- Withdrawal of consent or lost to follow-up,
- Disease progression,

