2.3 Dose escalation part/ Assessable for safety

The following patients will not be included in the population assessable for safety (primary analysis) and thus will be replaced:

- Patients who received $\leq 75\%$ RDI (Relative Dose Intensity) for trabectedin OR $\leq 75\%$ RDI for durvalumab over cycle 1, due to drug-related AE not considered as DLT.
- Patients who goes off treatment over cycle 1 for reasons unrelated to toxicity (DLT or any other AE), e.g. progression, lost to follow-up, will be replaced.

Population assessable for safety (primary analysis): all patients who completed the DLT assessment period or who developed DLT are included in the analysis.

CREATION OF A NEW INDICATOR VARIABLE

New binary variable TOL

Label: « Assessable for Safety»

TOL = 1 if the patient is assessable for safety (primary analysis)

TOL = 0 if the patient is not assessable for safety (primary analysis)

Criteria	eFORM variable	Control / program
Patient received $\leq 75\%$ RDI (Relative Dose Intensity) for trabectedin OR $\leq 75\%$ RDI for durvalumab over cycle 1, due to drug-related AE not considered as DLT	CYCLE 1 – DAY 1 AND DAY 2 (WEEK1) TREATMENT Trabectedin DOSE_TRA (dose) VPRE_TRA (volume of preparation) VOL_TRA (administered volume) WHY_TRA (2=AE related to treatment) Durvalumab DOSE_DU VPRE_DU VOL_DU WHY_DU DOSE-LIMITING TOXICITY FORM DLT_CYC OCC_CYC REL_ST	IF Trabectedin $((\text{Dose effectivement reçue VPRE_TRA and VOL_TRA/DOSE_TRA}) \leq 75\% \text{ AND INT_TRA} = 1 \text{ AND WHY_TRA} = 2 \text{ AND DLT_CYC} = 0)$ OR Durvalumab $((\text{Dose effectivement reçue VPRE_DU and VOL_DU / 1120 mg}) \leq 75\% \text{ AND INTER_D} = 1 \text{ AND WHY_DU} = 2 \text{ AND DLT_CYC} = 0)$ THEN TOL = 0
Patient goes off treatment over cycle 1 for reasons unrelated to toxicity (DLT or any other AE), e.g. progression, lost to follow-up	DISCONTINUATION VISIT END OF TREATMENT / end of treatment form DT_SOT DT_EOT EOTREASO DISCONTINUATION VISIT END OF TREATMENT / visit DIS_TRT TRA_EOT DUR_EOT DOSE-LIMITING TOXICITY FORM DLT_CYC AE FORM NUMAE AEVENT DT_AE MAX_INT TRA_MOD DUR_MOD	$\text{DT_EOT-DT_SOT} \leq 21 \text{ days}$ AND EOTREASO NOT IN (4 12) AND DLT_CYC=0 Additional control if $\text{DT_EOT-DT_SOT} \leq 21 \text{ days}$ 
 - Listing Other reason - Listing visit of end of treatment: DIS_TRT / TRA_EOT / DUR_EOT - Listing AE with TRA_MOD IN=3 OR DUR_MOD=3 THEN TOL=0

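### In the escalation part, under-dosed patients are replaced only when a drug-related event caused the shortfall; the others count as DLT-free observations of the combination

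*Protocol*

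**What the plan says.** Protocol 9.2.1 names two groups who are left out of the primary safety population and replaced.

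- The first is defined by low relative dose intensity (RDI), at or below 75% of either drug. For durvalumab the wording is "RDI for durvalumab over cycle 1, due to drug-related AE not considered as DLT", and the same cause is required for trabectedin.
- The second is defined by early departure, whatever the dose received: "Patients who goes off treatment over cycle 1 for reasons unrelated to toxicity (DLT or any other AE), e.g. progression, lost to follow-up".

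SAP 2.3 repeats both and adds a positive definition: "all patients who completed the DLT assessment period or who developed DLT are included in the analysis". That sentence concerns observation and sets no minimum dose.

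SAP 2.3 then codes the population as `TOL`. For low dose, `TOL` = 0 needs four things together: the received fraction at or below 75%, the interruption flag (`INT_TRA` or `INTER_D`) equal to 1, reason code 2 (the SAP labels it "WHY_TRA (2=AE related to treatment"), and no DLT. For leaving treatment, it tests `DT_EOT` minus `DT_SOT` at or below 21 days, "AND EOTREASO NOT IN (4 12) AND DLT_CYC=0".

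On timing, Protocol 3.3.2 says "All 3 patients within a dose level will be observed during 21 days (the period of observation of DLTs"); only then may the next level accrue. In Protocol 3.2 a DLT must begin within 21 days, and two criteria depend on duration, for example "Grade-3 hematologic toxicity lasting for > 7days".

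**The concern.** A 3+3 decision assumes that each patient counted without a DLT was exposed to the regimen under test. The low-dose rule makes that depend on why the dose was missed, but the reason does not alter the exposure. A patient whose durvalumab was omitted for an unrelated illness or a logistical problem is as uninformative about the combination as one whose dose was withheld for a drug-related event. Only the second is replaced.

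The error runs in one direction, because an under-exposed patient can only lower the apparent DLT rate. The MTD is part of the primary objective and sets the trabectedin dose for all 30 expansion patients, and each decision rests on three to six patients.

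The code adds a second gap. A dose that was never started need not carry an interruption flag. Durvalumab withheld on Day 2 for a drug-related event, which the protocol text says leads to replacement, could therefore stay `TOL` = 1. SAP 2.4 uses the administered flags (`ADMI_TRA`, `ADMI_DUR`) for the efficacy population; SAP 2.3 does not.

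**Working it through.** **The plan's own figures.** Protocol 9.1.1: 3 levels × 6 patients = 18 assessable, 20 accrued. Both reproduce (18/0.90 = 20, although no 10% rate is stated for this part). The allowance for non-assessable patients is 20 − 18 = 2.

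**Who is caught by the rules** (cycle 1, no DLT):

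| Situation | Protocol 9.2.1 | SAP 2.3 code |
|---|---|---|
| Infusion cut short to ≤75%, drug-related event | Replaced | `TOL` = 0 |
| Durvalumab never started, drug-related event | Replaced | `TOL` = 1 if the interruption flag is not set |
| Durvalumab missed for another reason, stays on study | Kept | `TOL` = 1 |
| Leaves treatment for progression or loss to follow-up | Replaced | Depends on what `DT_EOT` records |

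**Effect on escalation.** The documents give no escalation probability. Under 3.3.2 a level is passed with 0/3, or with 1/3 followed by 0/3. With true DLT rate p:

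P(escalate) = (1−p)³ + 3p(1−p)² × (1−p)³

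At p = 1/3: 0.296 + 0.444 × 0.296 = **0.428**.

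Now let one of the first three carry risk rp instead of p:

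- P(0/3) = (1−p)²(1−rp)
- P(1/3) = 2p(1−p)(1−rp) + (1−p)²rp
- P(escalate) = P(0/3) + P(1/3) × (1−p)³

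At p = 1/3, r = 0.5: 0.370 + 0.444 × 0.296 = **0.502**.

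At p = 1/3, r = 0: 0.444 + 0.444 × 0.296 = **0.576**.

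| True DLT rate (assumed) | All exposed | One at half risk | One at zero risk (bound) |
|---|---|---|---|
| 1/3 | 0.428 | 0.502 | 0.576 |
| 0.40 | 0.309 | 0.386 | 0.464 |
| 0.50 | 0.172 | 0.242 | 0.312 |

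**The off-treatment check.** Protocol 4.4 dates treatment discontinuation so that it "is defined as 30 days after the day of the last treatment administration", unless a new therapy starts. If `DT_EOT` follows that convention, a limit of 21 days can be met only when a new therapy starts. If `DT_EOT` is the last infusion date, the check also removes some patients who stopped after one cycle but completed day 21. The SAP does not say which applies. Reason 12, labelled in SAP 2.4 as progression with adverse events, is exempt; code 4 is not labelled.

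**The 21-day gate.** A grade 3 event starting on day d can be judged against the 7-day criterion only at about day d + 7. For d = 15 to 21 that falls after day 21, which is 7/21 = 1/3 of possible onset days. Assume that half of DLTs are of this type, that onset is uniform, and that only the last patient of each group of three is pending and is counted as having no DLT. That patient's risk is then 1/3 × (1 − 0.5/3) = 0.278:

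- P(0/3) = 4/9 × 0.722 = 0.321
- P(1/3) = 4/9 × 0.722 + 4/9 × 0.278 = 0.444
- P(escalate) = 0.321 + 0.444 × 0.321 = **0.464**

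If the duration-type share runs from a quarter to all, the result runs from 45% to 50%.

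**The case against.** Several points on the other side are sound.

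- **The patient would be visible.** SAP Appendix 1 lists both doses, interruptions and both RDIs per patient for each dose-level report. The steering committee meets before each escalation and settles DLT-status questions, and the IDMC is asked to approve the MTD. This stands as mitigation. It does not close the gap, because no written rule tells either body to discount an under-exposed patient, and the primary analysis uses `TOL` = 1.
- **It should be uncommon.** The schedule of assessments shows a 24-hour stay over Days 1–2, which makes a purely logistical miss less likely, although Protocol 6.3 allows outpatient treatment. The frequency is unknown.
- **Zero risk is too pessimistic.** Trabectedin is the escalated drug, and a patient who misses durvalumab has still received it. The 58% is therefore a bound and not an expectation.
- **The code is pseudo-code and the CRF is not shown.** Whether an omitted dose passes depends on how the interruption and reason fields are completed.

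A reader might go further and infer that patients not followed to day 21 are routinely counted as DLT-free. The documents do not support that: the second exclusion, the 21-day rule in 3.3.2 and the SAP's sentence on the completed assessment period largely cover it. The `DT_EOT` ambiguity does not establish it either, since the documents do not settle the date convention and one of the two readings removes patients instead of counting them. Nor does the late-onset issue justify a large figure. A rise to 54% needs every patient to be pending at the gate and every pending event to be missed for good. The DLT definition rests on onset, so a late event that lasts long enough is still a DLT.

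**Conclusion.** The low-dose exclusion is wrong as written. In both documents it depends on the cause of the shortfall, and the SAP sets no minimum dose, so a patient under-dosed for another reason can enter the MTD decision as DLT-free. The SAP code is narrower than the text it implements.

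The direction, towards escalation, is certain. The size rests on assumptions: with one such patient among the first three and a true DLT rate of 1/3, the escalation probability rises by about 7 points at half risk and by 15 points at most. One patient shifts the odds but does not by itself decide the outcome.

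The off-treatment code and the timing of the 21-day gate are secondary. Both need reconciling. The gate's effect is about 3 points (43% to 46%) if only the last patient is pending.

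**What to change.** 1. **Protocol 9.2.1 and SAP 2.3:** treat any patient without a DLT who received at or below 75% RDI of either drug in cycle 1, for any reason, as not assessable and replace them. Keep every patient with a DLT.
2. **`TOL` code, dose:** compute the received fraction from the administered flags and volumes, count a dose not given as 0%, and drop the interruption and reason-code conditions.
3. **`TOL` code, observation:** replace the `DT_EOT` test by the last DLT-assessment date compared with day 21. The code then matches the SAP's own definition and no longer depends on the date convention in Protocol 4.4 or on end-of-treatment reason codes.
4. **Secondary:** reconcile the 21-day accrual gate in 3.3.2 with the duration-based DLT criteria in 3.2, and state how a patient whose grade 3 event is still unresolved at day 21 is classified when the committee meets.

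The cost is a wording and code change on data already collected. There may be an occasional extra replacement against an allowance of two, so the stated maximum of 20 could be exceeded and should be reviewed. Depending on how item 4 is settled, there may be a short wait when a late event is ongoing.

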9.2.2. Phase I (Expansion cohorts)

- Eligible population: All patients included without major violation of eligibility criteria.

- Population assessable for efficacy: All patients eligible and for whom the following conditions are satisfied:
 - Received at least one complete or two incomplete treatment cycles,
 - At least one disease measurement recorded not less than six weeks after treatment onset.
- The following patients will also be included in the population assessable for efficacy; they will be considered as "inevaluable for response" for the primary endpoint as per RECIST v1.1 criteria (i.e. objective response under treatment) and not be replaced in the primary efficacy analysis:
 - Any eligible patients who received at least one treatment cycle or two incomplete treatment cycles and experience disease progression or die due to disease progression prior to response evaluation (will be considered as "inevaluable for response" due to early progression).
 - Patients withdrawn due to drug-related toxicity without any tumor assessments after the start of study treatment (will be considered as "inevaluable for response" due to toxicity).
 - Patients who received at least one administration of the treatment AND withdrawn due to significant clinical deterioration of unknown reason AND without any tumor assessments after the start of study treatment (will be considered as "inevaluable for response" due to significant clinical deterioration).
- Safety population: all patients having received at least one (any) treatment administration.

Patient's replacement:

- Any patient not eligible or not assessable for efficacy will be replaced.
- However, any patient who received at least one administration of the study drug will be included in the safety analysis.

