9.1.1. Phase I (Expansion cohorts)

- The primary objective is to determine preliminary signs of anti-tumor activity of trabectedin given in combination with DURVALUMAB among two selected cohorts of patients (STS and ovarian carcinomas) in terms of objective response under treatment as per RECIST v1.1 criteria.
- Once the Maximum Tolerated Dose (MTD) is established for trabectedin, 2 distinct cohorts will be treated at the MTD:
 - Cohort A: patients with advanced STS.
 - Cohort B: patients with advanced ovarian carcinomas
- For each cohort:
 - Sample size is calculated based on the first stage of a 2-stage Gehan design assuming a 20% efficacy rate, 5% false positive rate and 10% precision (Gehan 1961).
 - 14 eligible and assessable subjects are required.
 - If at least one objective response (CR or PR as per RECIST v1.1) is observed under treatment, the study drug association will be considered worthy of further testing in this indication.

Assuming 10% patients not eligible or that cannot be assessed for the primary endpoint, **15 patients will be recruited for each of the 2 cohorts**, i.e. a total of **30 patients will be included in the expansion cohorts**.

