APPENDIX 3: EVALUATION OF RESPONSE. THE RECIST

Response and progression will be evaluated in this study using the new international criteria proposed by the revised Response Evaluation Criteria in Solid Tumors (RECIST) guideline (version 1.1) [Eur J Ca 45:228-247, 2009]. Changes in only the largest diameter (unidimensional measurement) of the tumor lesions are used in the RECIST criteria.

DEFINITIONS

Evaluable for toxicity: All patients will be evaluable for toxicity from the time of their first treatment with study drugs.

Evaluable for objective response: Only those patients who have measurable disease present at baseline, have received at least one cycle of therapy, and have had their disease re-evaluated will be considered evaluable for response. These patients will have their response classified according to the definitions stated below. (Note: Patients who exhibit objective disease progression prior to the end of cycle 1 will also be considered evaluable.)

DISEASE PARAMETERS

Measurable disease. Measurable lesions are defined as those that can be accurately measured in at least one dimension (longest diameter to be recorded) as ≥ 20 mm by chest x-ray, as ≥ 10 mm with CT scan, or ≥ 10 mm with calipers by clinical exam. All tumor measurements must be recorded in millimeters (or decimal fractions of centimeters).

Note: Tumor lesions that are situated in a previously irradiated area are not considered measurable.

Malignant lymph nodes. To be considered pathologically enlarged and measurable, a lymph node must be >15 mm in short axis when assessed by CT scan (CT scan slice thickness recommended to be no greater than 5 mm). At baseline and in follow-up, only the short axis will be measured and followed.

Non-measurable disease. All other lesions (or sites of disease), including small lesions (longest diameter <10 mm or pathological lymph nodes with ≥ 10 to <15 mm short axis), are considered non-measurable disease. Bone lesions, leptomeningeal disease, ascites, pleural/pericardial effusions, lymphangitis cutis/pulmonitis, inflammatory breast disease, and abdominal masses (not followed by CT or MRI), are considered as non-measurable.

Note: Cystic lesions that meet the criteria for radiographically defined simple cysts should not be considered as malignant lesions (neither measurable nor non-measurable) since they are, by definition, simple cysts.

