		$((C2_ADMI_TRA = 1 \text{ or } C2_ADMI_DUR = 1) \text{ and } (C2_VOL_TRA > 0 \text{ or } C2_VOL_TRA > 0))$ Additional control: Date of start cycle Total dose given during cycle Therapy changes during cycle AND

 one disease measurement recorded not less than six weeks after treatment onset 	TUMOR ASSESSMENT (TUM_CYC) DIS_EVA (1=week 6) DT_MEAC	DIS_EVA =1 and Information on tumor assessment completed and date of tumor assessment OR IF
❖ Received at least one treatment cycle and experience disease progression or die due to disease progression prior to response evaluation after the start of study treatment	CYCLE 1 – DAY 1 AND DAY 2 (WEEK1) ADMI_TRA (1=Done) ADMI_DUR (1=Done) TREATMENT (EOTRT) EOTREASO (1=Disease progression and 12=Disease progression and Adverse event(s)) END OF STUDY (EOS) REA_STUD (3=Death) DT_DEATH CA_DEATH (1= Progression of disease) TUMOR ASSESSMENT (TUM_CYC) DT_MEAC (Date of measurement)	(C1_ADMI_TRA = 1 and C1_ADMI_DUR = 1) Additional control: Date of start cycle Total dose given during cycle Therapy changes during cycle AND $((EOTREASO \text{ in } (1 \text{ 12}) \text{ or } (CA_DEATH=1 \text{ and } EOS_REA = 3)) \text{ and } DT_MEAC \text{ is blank})$ OR IF
❖ withdrawn due to drug-related toxicity without any tumor assessments after the start of study treatment	DISCONTINUATION VISIT TRA_EOT (0=toxicity) DUR_EOT (0=toxicity) TUMOR ASSESSMENT (TUM_CYC) DT_MEAC (Date of measurement)	DT_MEAC is blank AND TRA_EOT =0 or DUR_EOT=0 OR IF
❖ Patients who received at least one administration of the treatment AND withdrawn due to significant clinical deterioration of unknown reason AND without any tumor assessments after the start of study treatment	TUMOR ASSESSMENT (TUM_CYC) DT_MEAC (Date of measurement) DISCONTINUATION VISIT END OF TREATMENT (EOTRT) DT_SOT, DT_EOT (start and end of treatment) EOTREASO (8= General or specific changes in patient's condition) ADVERSE EVENT FORM (AEV) DT_AE, DTENDAE (start and end date) TRA_MOD (3= Definitively stopped) DUR_MOD (3= Definitively stopped) TRA_REL (2= Unrelated) DUR_REL (2= Unrelated)	DT_MEAC is blank EOTREASO = 8

- Safety population: all patients having received at least one (any) treatment administration

CREATION OF A NEW INDICATOR VARIABLE

Patients will be evaluable for safety if they have received at least one treatment administration. (SAF=1).

New binary variable ELI_DLT

Label: « Safety population»

SAF=1 if the patient is assessable for safety

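### Protocol text, Appendix 3 and SAP code disagree on who enters the expansion ORR denominator, and some low-exposure early progressors are dropped and replaced

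*Protocol*

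**What the plan says.** Protocol 9.2.2, repeated in SAP 2.1.2 and 2.4, makes an eligible patient assessable for efficacy after one complete or two incomplete cycles plus a disease measurement at six weeks or later. Three further groups stay in the denominator as inevaluable for response:

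- **Early progression:** "Any eligible patients who received at least one treatment cycle or two incomplete treatment cycles and experience disease progression or die due to disease progression" before response evaluation.
- **Toxicity:** withdrawal for drug-related toxicity with no post-baseline scan. No minimum exposure is stated.
- **Deterioration:** "Patients who received at least one administration of the treatment AND withdrawn due to significant clinical deterioration of unknown reason", again with no scan.

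For everyone else the rule is: "Any patient not eligible or not assessable for efficacy will be replaced".

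Appendix 3 adds a note on evaluability for response: "Patients who exhibit objective disease progression prior to the end of cycle 1 will also be considered evaluable".

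SAP 2.4 turns these clauses into the indicator `ELI_EFF`. The condition "C1_ADMI_TRA = 1 and C1_ADMI_DUR = 1" appears in both exposure branches and in the early-progression branch. It does not appear in the toxicity or deterioration branches.

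SAP 3.2.2 bases the primary ORR on the eligible and assessable population. The expansion table in SAP 3.2.3 is headed with the filter `TOL=1`. `ELI_EFF=1` is named only in SAP 3.2.4, for the secondary endpoints.

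**The concern.** Whether a patient enters the denominator of the primary ORR should not depend on which passage the programmer follows. Here three sources give different answers for the same patient.

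The text holds documented disease failure to a stricter exposure test than toxicity or unexplained deterioration. A patient who falls through that gap is replaced by a new patient with a fresh chance of response. This bears on the reported ORR and its interval. It also bears on the go rule, which is met "If at least one objective response (CR or PR as per RECIST v1.1) is observed under treatment", because each replacement adds an attempt at that single response.

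**Working it through.** **The plan's own figure.** Protocol 9.1.1 states: "Sample size is calculated based on the first stage of a 2-stage Gehan design assuming a 20% efficacy rate, 5% false positive rate and 10%" (the last figure being the margin sought). The number needed per cohort is given as: "14 eligible and assessable subjects are required". The first-stage size is the smallest n with (1 − 0.20)^n ≤ 0.05. Since 0.8^13 = 0.055 and 0.8^14 = 0.044, n = 14. The stated figure reproduces, and nothing below changes it.

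**Clauses against code.** Each row applies Protocol 9.2.2 on its natural reading, then the `ELI_EFF` logic of SAP 2.4, to one type of eligible patient.

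| | Patient | Protocol text | SAP code |
|---|---|---|---|
| 1 | Both drugs partly infused in cycle 1, progression, no cycle 2, no scan | out | in |
| 2 | As 1, but progression recorded on a scan not coded week 6 | out | out |
| 3 | No durvalumab in cycle 1, progression or death from it, no cycle 2, no scan | out | out |
| 4 | No durvalumab in cycle 1, full cycle 2, week-6 scan | in | out |
| 5 | No durvalumab in cycle 1, incomplete cycle 2, progression, no scan | in | out |
| 6 | Full cycle 1, progression on a scan not coded week 6 | in | out |
| 7 | Both drugs partly infused in cycle 1, durvalumab only in cycle 2, week-6 scan | in | out |
| 8 | No durvalumab in cycle 1, toxicity withdrawal, no scan | in | in |
| 9 | No durvalumab in cycle 1, clinical deterioration, no scan | in | in |
| 10 | Full cycle 1, progression, no scan | in | in |

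Reasons for the code results:

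- Row 1: the progression branch asks whether both drugs were administered and does not compare prepared with infused volume.
- Rows 2 and 6: the main branch needs `DIS_EVA=1` (week 6) and the progression branch needs a blank `DT_MEAC`. An earlier scan date fails both.
- Rows 3 to 5: `C1_ADMI_DUR=1` fails in every branch that could admit the patient.
- Row 7: the cycle-2 volume test reads `C2_VOL_TRA` twice and never `C2_VOL_DUR`.

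**The filter on the primary table.** SAP 2.3 defines `TOL` for the dose-escalation part. It sets `TOL=0` when treatment ends within 21 days for a reason other than toxicity, such as progression, without a DLT. Applied to the expansion cohorts, it would remove progressors who stop in cycle 1 by another route.

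**Size.** The documents give no frequency for these patients. Assume k dropped non-responders per cohort, each replaced so that 14 are assessable, and 3 responders among the 14. Exact 95% limits are in brackets.

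- As reported: 3/14 = 21.4% (4.7–50.8).
- With k = 1 restored: 3/15 = 20.0% (4.3–48.1). Relative inflation is 15/14 − 1 = 7.1%.
- With k = 2 restored: 3/16 = 18.8% (4.0–45.6). Relative inflation is 16/14 − 1 = 14.3%.

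For the go rule, let r be the response rate among the other patients. If the k non-responders count among the 14, the chance of at least one response is 1 − (1 − r)^(14−k). If they are replaced, it is 1 − (1 − r)^14.

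| r | k = 2, kept | k = 1, kept | replaced |
|---|---|---|---|
| 10% | 1 − 0.9^12 = 71.8% | 1 − 0.9^13 = 74.6% | 1 − 0.9^14 = 77.1% |
| 20% | 1 − 0.8^12 = 93.1% | 1 − 0.8^13 = 94.5% | 1 − 0.8^14 = 95.6% |

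**Opposite direction.** A row-4 patient may be a responder. If one of three responders is dropped by the code and replaced by a non-responder, 3/14 = 21.4% becomes 2/14 = 14.3%.

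**The case against.** A prespecified response-evaluable population is a legitimate choice for a descriptive Gehan first stage without p-values, and the plan already counts three groups of failures as non-responders. The early-progression clause does not say that its one cycle must be complete, and the code reads it as a started cycle (row 1). The affected patient needs an incomplete first cycle, no countable second cycle, and progression rather than toxicity or deterioration. Both drugs are given on consecutive days of one hospital stay, to patients with ECOG ≤ 1 and life expectancy above three months, so this should be uncommon. SAP 2.4 also lists manual checks of dates, doses and therapy changes that might catch the duplicated variable.

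Much of this stands as a limit on size. It does not remove the inconsistency. The contrast with two incomplete cycles implies that the single cycle is a complete one, and if the code's reading is the intended one, the text should say so. The manual checks carry no rule for overriding `ELI_EFF`.

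A reader might infer more: that the primary ORR systematically excludes treatment failures or poorly tolerating patients, that everyone without cycle-1 durvalumab is dropped, or that the bias always runs upward. The documents do not support this. Toxicity and deterioration withdrawals without a scan are kept (rows 8 and 9), the code is looser than the text in row 1, and row 4 can remove a responder. Because of the `TOL=1` heading, it is also unclear whether `ELI_EFF` governs the coded primary ORR at all.

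**Conclusion.** The point holds as an inconsistency in the definition and coding of the primary denominator. On the natural reading of Protocol 9.2.2, a patient who progresses or dies of progression after one incomplete cycle is dropped and replaced, against Appendix 3 and out of line with the two neighbouring clauses. The `ELI_EFF` code departs from the text in both directions, and the primary table names a different filter.

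The effect is modest: about 1.4 to 2.7 percentage points on the ORR for one or two dropped non-responders with three responders, well inside an interval of roughly 5% to 51%. With two such patients, the chance of meeting the go rule changes by about 5 points at a 10% response rate in the others and by about 2.5 points at the plan's 20%. These figures assume that every dropped patient is a non-responder and is replaced. They do not describe row 4, where the bias can be downward. The number of affected patients is unknown. The correction is worth making because it is small and settles the primary result.

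**What to change.** 1. **Protocol 9.2.2 and SAP 2.1.2/2.4.** Reword the early-progression clause to cover any eligible patient with at least one administration of study treatment who progresses, or dies of progression, before response evaluation. Count these patients as non-responders and do not replace them. This uses the threshold of the deterioration clause and agrees with the Appendix 3 note.
2. **SAP 2.4, exposure test.** Accept any cycle with both drugs fully given, or at least two cycles with any `VOL_TRA>0` or `VOL_DUR>0`. Correct the second `C2_VOL_TRA` to `C2_VOL_DUR`.
3. **SAP 2.4, progression branch.** Replace `C1_ADMI_TRA=1` and `C1_ADMI_DUR=1` with any `VOL_TRA>0` or `VOL_DUR>0`, and remove the blank-`DT_MEAC` requirement. The branch then decides membership only; the response category still comes from the centrally reviewed assessments.
4. **SAP 3.2.3.** Replace `TOL=1` with `ELI_EFF=1` for the expansion ORR.
5. Keep the exposure-restricted rate as a sensitivity analysis.

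The cost is one clause and a few lines of code. No extra patients are needed, and there may be fewer replacements. The downside is that the reported ORR may be slightly lower.
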